For purposes of comparison to MEG resting state, echo-planar imaging-gradient recalled echo (EPI-GRE) data normally acquired during functional MRI scanning (fMRI) will be acquired during the MRI session. Subjects will simply rest in the prone position with their eyes open for 2 minutes and closed for 2 minutes. The 10 minute baseline MRI scan will allow us to compare the generators of resting state MEG gamma-band to resting state activation in fMRI.

The total MRI procedure, if patients consent to the additional sequences, will last approximately 70 minutes and will begin with the anatomical portion. In case the study subjects feel any discomfort anytime after this first acquisition, they will be freed of terminating the additional scans without being disqualified from the study.

MEG Data Collection: Magnetic field data will be recorded using a whole head neuromagnetometer (4D Neuroimaging) with an array of 248 sensors at rest with eyes open for 2 minutes and closed for 2 minutes at a 678 Hz sampling rate. Data will be processed offline using a 0.1-100 Hz band pass filter. Data will be manually examined and five 6-second artifact free epochs for both eye-open and closed conditions will be selected for further analyses. Artifact correction if needed will be performed using independent components analysis.¹⁰⁸ Sensors will be realigned to a common sensor array to allow group level analysis in a shared brain space.¹⁰⁹

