MEG Data Processing: Following data acquisition, there are 4 major steps for graph theory analysis.⁶³ First, data will be transformed into the frequency domain using Morlet wavelets and parceled into six standard frequency bands: delta (1-4 Hz), theta (4-8 Hz), alpha (8-12 Hz), low beta (12-20 Hz), high beta (20-30 Hz) and gamma (30-60 Hz).¹¹⁰ Further analyses will be performed separately for each band. Second, the strength of functional connectivity must be calculated between all sensors. Granger causality will be used for this step, providing a directional weighted measure of connectivity suitable for graph theory.^{111, 112} Third, functional connections between nodes will be used to create a network graph. This is matrix representing the directed weighted connection strengths between all sensors for each frequency band. Advantages of creating a weighted network graph include ensuring full connectedness and avoiding potentially arbitrary thresholds required for binary networks.⁶¹ Finally, graph analyses can be performed on the network graph using the Matlab-based Brain Connectivity Toolbox⁶¹ and custom Matlab code. Our *primary MEG outcome measure* will be network small-worldness, calculated as the ratio of the mean clustering coefficient to the mean path length normalized to a randomly connected network.¹¹³ *Planned secondary MEG outcome measures* will include global efficiency (a measure of global integration related to path length), nodal efficiency (a measure of modularity)⁶⁰, and degree distribution (a measure of network resilience)¹¹⁴.

B. Description of Population to be Enrolled:

We will enroll 25 PD subjects over the age of 40 without cognitive impairment diagnosed with probable PD using UK Brain Bank Criteria³⁸ and 55 PD subjects over the age of 40 with MCI or mild dementia using the Movement Disorder Task Force 2012 criteria and a Clinical Dementia Rating scale score (CDR) less than 2.^{39, 40} All study visits will be performed in subjects' best dopaminergic On state. PD MCI and mild dementia subjects will be tested on anticholinesterase therapy if already taking these medications given the potential difficulty of finding drug naïve subjects; long half-life of these medications; and desire to find measures robust to medication effects as seen in prior MEG studies.⁴¹

Exclusion criteria:

- 1) features suggestive of other neurological disorders
- 2) DBS
- 3) evidence for active depression or Hospital Anxiety Depression Scale⁴² score \geq 11

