relationship between network connectivity and cognitive function. The data generated by this Aim will fundamentally advance our understanding of the role of cortical physiology in PD cognitive dysfunction, will provide a modern network framework for future studies in this field and may provide insights leading to future therapeutic targets.

Aim 2 Rationale and Design: While finding group differences or clinical associations in brain connectivity using MEG will improve our understanding of the pathophysiology of PD cognitive dysfunction it is unlikely to provide sufficient discriminant ability to serve as a useful diagnostic or predictive biomarker. Machine learning algorithms offer several advantages in terms of biomarker development including: 1) Characterization of data at the level of the individual; 2) Ability to simultaneously optimize multiple features from complex datasets; and 3) Allows data to drive feature selection rather than theoretical assumptions.⁷² Support Vector Machine (SVM) is a machine learning method that works by determining the maximum separation between classes in a high dimensional space composed of the features of interest.¹¹⁹ Our *objective* for this Aim is to develop a novel state-defining biomarker for PD-MCI based on MEG measures of regional activity and network connectivity using SVM. We *hypothesize* that cognitive dysfunction in PD can be characterized through a unique combination of MEG regional and network features and optimized through SVM. To test this hypothesis, we will reanalyze the MEG data collected in Aim 1 using SVM to classify PD patients with and without MCI.

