All subjects will be required to wear hearing protection and will be supervised by study personnel during all aspects of this study. A neurologist will be available either in person or on-call within the building in the event of a seizure or other adverse study event. Study personnel involved in human subject interactions will be trained not only in human subjects protection but will be also BLS or ACLS certified and specifically trained in seizure safety and what to do in the event of other medical emergencies. There is a COR cart available outside of the TMS and MEG laboratories. All adverse events will be reported to the IRB within 5 days and seizures or other significant adverse events associated with TMS will additionally be reported to the FDA.

E. Potential Scientific Problems:

Prior TMS trials are often questioned regarding the adequacy of patient blinding with certain sham procedures. Our sham involves both auditory and tactile stimulation, and in fact resulted in a similar improvement in depression as real TMS in our recent trial.¹⁹ Subject retention, particularly with PD-MCI, may be difficult with 2 weeks of daily treatment. We will use similar procedures to our PD apathy rTMS trial where we maintained 100% retention. Finally, our sample size is relatively small to detect clinically significant changes. This is in part due to budgetary limitations and one goal of this trial is to serve to develop a more definitive, larger trial with longer-term follow-up. Changes in sensor location over repeated recordings may result in false attribution of brain activity

changes. To address this issue, sensors will be realigned to a common sensor array to allow repeated group level analysis in a shared brain space.¹⁰⁹

F. Data Analysis Plan:

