AIM 1 Statistical Analysis and Sample Size: To address our primary research question, Spearman correlations will be used to identify frequency spectra small-worldness measures associated with the MDRS in eyes-closed data with a false detection rate set at 0.05 to handle the issue of multiple comparisons. We will then use linear regression to determine whether small-worldness in these specified frequency bands remain associated with the MDRS when controlling for each other as well as other important covariates, namely age and motor severity. A *sample size* of 45 (allowing for 5 drop-outs and/or unusable data-sets from the original 50) will allow us to detect correlations of 0.18 or higher between our MEG features and MDRS with 80% power 0.05 significance. This is comparable to correlations of 0.19 and higher seen in other resting state MEG studies of cognition.¹¹⁵ Planned secondary analyses will parallel our primary analysis to determine whether global efficiency, nodal efficiency or degree distribution are significantly associated with MDRS in linear regression models. Exploratory analyses will assess reactivity of these measures between eyes open and closed conditions and assess whether domain specific neuropsychological test scores are associated with connectivity within networks defined by domain related nodes (e.g. occipital nodes and visuospatial tests).

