AIM 2 Statistical Analysis and Sample Size: We will use SVM to determine what combination of MEG features yields the most robust classifier for discriminating PD with and without MCI. The principle behind SVM learning is that features of interest can be modeled in a high-dimensional feature space (see Figure 2 for a visualization of a very simple 2 feature space). SVM then uses a recursive algorithm to define a hyper-plane of select features creating the greatest distance between groups of interest.¹¹⁹ Given the large potential combination of MEG features and sensors this will be a computationally intensive but tractable SVM application. As the optimal number of features to build an SVM classifier is not known a priori, we will use a procedure called bagging-cross-validation to determine the optimal number of features and maximize the information gained from SVM in this relatively small sample size.¹²¹ This approach uses a boot-strap leave one out procedure to create $n - 1$ training sets and n test subjects, where n is the total sample size, to optimize feature number and maximize the final receiver operating curve. Given the large effect sizes seen in our pilot data and other MEG studies of PDD⁵⁸, we anticipate that our *sample size* of 45 (allowing for 5 unusable data-sets from the original 50) will allow us to create a classifier with an area under the ROC curve (AUC) of 0.95 or higher comparable to AUCs seen in other SVM applications in dementia and MCI populations with as few as 15 subjects per group.⁶⁸

AIM 3 Statistical Analysis and Sample Size: We will address our primary clinical research question by determining whether there is a significant group difference between the real and sham treated PD-MCI patients on the MDRS change following rTMS using repeated measures ANOVA. We will address our primary physiologic research question by determining whether there is a significant difference between the real and sham treated PD-MCI patients on change in MEG measures of small-worldness using a repeated measures ANOVA. Planned secondary analyses will include determining group differences in change on measures of quality of life, domain specific neuropsychological results and durability at the 28-day post-TMS time point. If cognition is improved we will use regression modeling to determine if these improvements were associated in changes

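### MEG epochs are picked by hand with no rule for choosing among clean ones and no masking of the selector, so the primary MEG outcome is exposed to selection bias of unknown size

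*Combined protocol and SAP*

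**What the plan says.** Section IV.A, MEG Data Collection, records each subject "at rest with eyes open for 2 minutes and closed for 2 minutes at a 678 Hz sampling rate". It then reduces the recording by hand: "Data will be manually examined and five 6-second artifact free epochs for both eye-open and closed conditions will be selected". On cleaning it adds: "Artifact correction if needed will be performed using independent components analysis". It gives no artifact threshold, no trigger for the correction, and no order of correction relative to selection.

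The selected data feed all three aims:

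- **Primary MEG outcome** (IV.A, MEG Data Processing): it "will be network small-worldness, calculated as the ratio of the mean clustering coefficient to the mean path length normalized to a randomly connected network".
- **Aim 1** (IV.F): "Spearman correlations will be used to identify frequency spectra small-worldness measures associated with the MDRS in eyes-closed data".
- **Aim 2** (IV.C): "we will reanalyze the MEG data collected in Aim 1 using SVM to classify PD patients with and without MCI".
- **Aim 3** (IV.F): the test is for a "difference between the real and sham treated PD-MCI patients on change in MEG measures of small-worldness using a repeated measures ANOVA".

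The only discussion of blinding is in IV.E, Potential Scientific Problems, and it concerns patients: "Prior TMS trials are often questioned regarding the adequacy of patient blinding". The answer given there is the sham coil. No section says that the people who process MEG data are masked to anything.

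**The concern.** Being free of artifact is an entry condition. It decides which epochs are eligible, not which five of the eligible ones are used. Where more than five are clean, the choice is left to a person, and the plan does not prevent that person from knowing whether the subject has MCI or received real stimulation.

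The stake differs by aim:

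- **Aim 1** pools subjects with MCI and with normal cognition. A choice that differs by cognitive group would add to, or subtract from, the association between small-worldness and the MDRS.
- **Aim 2** tries to predict the group label. If the label influenced which epochs were kept, it is already in the features. The leave-one-out procedure in IV.F starts after that step, so each held-out subject carries the same leak.
- **Aim 3** compares change between arms. A choice that differs by arm on the post-treatment scan goes straight into the contrast. Randomization and patient blinding both act before that step and do not remove it.

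**Working it through.** The plan states no figure for this point, so there is none to reproduce.

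**1. Room for choice.** Inputs from IV.A: 2 minutes (120 s) per condition, 6-second epochs, five kept.

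- Maximum non-overlapping epochs: 120 / 6 = 20.
- Time used: 5 × 6 = 30 s, and 30 / 120 = 25% of the recording.

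Twenty is a ceiling before artifact rejection. The number of clean epochs, K, is not given, so a range is used.

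**2. Shift in the five-epoch mean.** Assume that the subject's value behaves like an average of five per-epoch values with between-epoch SD 1, and that the choice follows a score correlated ρ with each epoch's own value. Then

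shift = ρ × E(mean of the top 5 of K standard normal values).

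For example, with K = 20 and ρ = 0.3: 0.3 × 1.213 = 0.364. Simulated results (100,000 subjects per cell), in between-epoch SDs:

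| Clean epochs K | ρ = 0 | ρ = 0.1 | ρ = 0.3 | ρ = 0.5 | ρ = 1 (ceiling) |
|---|---|---|---|---|---|
| 5 | 0 | 0 | 0 | 0 | 0 |
| 8 | 0.00 | 0.06 | 0.17 | 0.28 | 0.55 |
| 10 | 0.00 | 0.08 | 0.22 | 0.37 | 0.74 |
| 15 | 0.00 | 0.10 | 0.31 | 0.52 | 1.03 |
| 20 | 0.00 | 0.12 | 0.36 | 0.61 | 1.21 |

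The K = 5 row follows without simulation: all five are used. Every ρ and K is an assumption.

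**3. Which knowledge matters in Aim 3.** Let D_R and D_S be the true mean changes under real and sham, and b_R and b_S the selection shifts on the post-treatment scan. The contrast estimates

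(D_R + b_R) − (D_S + b_S) = (D_R − D_S) + (b_R − b_S).

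A selector who knows visit but not arm has b_R = b_S in expectation, and the bias term is zero. A selector who knows arm can have b_R ≠ b_S. All Aim 3 subjects are PD-MCI, so cognitive group plays no part in this contrast.

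**4. What arm knowledge could do to the Aim 3 test.** Illustration only: 25 per arm (IV.F), no true effect, 20 clean epochs, picking applied to one arm's post-treatment scan alone, and a two-sided t-test on change at 0.05 (4,000 replicates).

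| Between-person SD of change (epoch SDs) | ρ = 0 | ρ = 0.1 | ρ = 0.3 | ρ = 0.5 |
|---|---|---|---|---|
| 0.5 | 0.051 | 0.09 | 0.35 | 0.76 |
| 1.0 | 0.049 | 0.07 | 0.19 | 0.43 |

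Entries are type I error rates. The SD ratios are also assumed. Fewer clean epochs give smaller shifts (step 2) and so less inflation. When choice is unrelated to outcome (ρ = 0), the nominal level is restored.

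**The case against.** The strongest reply is that the outcome cannot be seen in what the selector looks at. Small-worldness appears only after wavelet transformation, Granger causality between all sensors, graph construction and scaling to a random network. This is done separately in six bands, with nothing to suggest that epochs are chosen anew for each. Deliberate picking on the outcome would be hard, and a large ρ is unlikely. This stands. What remains is that visible features such as slowing or drowsiness might guide the choice and also relate to connectivity; that is a judgement, not something the protocol states.

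Three further limits also stand. The number of clean epochs is unknown. The plan does not say how the five epochs are combined, so the averaging model is an assumption. Between-epoch SD has no documented link to between-subject SD, so the shifts do not convert to an effect on any test without another assumption.

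Stronger readings are tempting, but the documents do not support them:

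- **That the selector will know group or arm, or that the results will be biased.** The plan is silent on masking, which leaves the risk open without showing that it occurs.
- **That knowing the visit is enough to bias Aim 3 despite the sham control.** Step 3 shows that such a shift cancels in expectation between arms.
- **That 1.21 SD is a plausible size.** It requires perfect ranking of 20 clean epochs by an unseen quantity.
- **That the bias would favour a particular direction by group.** Nothing in the protocol indicates one.

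**Conclusion.** The concern holds as a weakness of the stated method. Selection is manual, surplus clean epochs have no rule, and the selector is not masked to cognitive group (Aims 1 and 2) or arm (Aim 3). Leave-one-out validation and patient blinding do not close the gap. Knowledge of visit alone largely cancels in Aim 3; exact cancellation needs the shift not to depend on arm, for instance through differing numbers of clean epochs.

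The magnitude cannot be settled from the documents. For assumed choice-outcome correlations of 0.1 to 0.5 it runs from zero (five clean epochs), through 0.06 to 0.28 between-epoch SD (8 clean), to 0.12 to 0.61 (20 clean). These figures rest on the averaging model and on a selector who knows group or arm. The change is worth making because it protects the primary MEG outcome at little cost, not because a large bias has been demonstrated.

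**What to change.** In IV.A, MEG Data Collection, replace free manual choice with a fixed rule. For example: after artifact marking and any independent components correction, take the first five clean 6-second epochs in time order for each condition. Other pre-set rules that ignore the outcome would also serve. State the artifact criterion and what triggers the correction.

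Carry out the marking and the correction decisions on files coded to hide cognitive group and arm, and visit as a precaution. Both parts are useful. Masking removes the influence of expectation by group and arm. The order rule makes the choice reproducible and limits discretion if masking is imperfect. An order rule alone would leave artifact marking to an unmasked person.

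The cost is a file-coding step, done by someone other than the selector, and a few sentences of text. The plan also gives up the freedom to prefer later epochs. No recording, visit or sample size changes.

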- 4) motor symptoms expected to interfere with scanning
- 5) contraindications to TMS:
 - history of seizures or status epilepticus,
 - unstable coronary artery disease
 - hydrocephalus
 - implantable electrodes, cerebral spinal fluid shunts, skull plates or other intracranial metal
 - medical devices including pacemakers or other implantable stimulators or pumps
 - subjects taking medications known to lower seizure threshold
 - pregnancy

In order to complete recruitment including consent screen failures, drop-outs and unusable datasets we request the capacity to recruit up to 150 participants.

C. Study Design and Research Methods

Aim 1 Rationale and Design: Even while not engaged in a task the brain exhibits spatially and temporally organized patterns of activity.⁸⁴ The past 15 years has seen remarkable progress in understanding these intrinsic functional networks (also termed resting-state networks) in both health and disease.⁸⁵ Intrinsic networks are consistent within and across individuals, correlate with behavioral and clinical outcomes, and can be analyzed with graph theory measures to define global and local aspects of network organization.⁵⁹ MEG can be used to identify multiple intrinsic networks similar to fMRI but with additional information regarding the power spectra of connections.^{86, 87} Importantly, MEG measures of intrinsic activity can sensitively discriminate AD from other neurological disorders and correlate with cognitive function in both AD and multiple sclerosis.^{40, 47, 64} Prior studies of PD suggest changes in cortical connectivity may be associated with dementia but did not define network organization using graph theory.⁸⁸ Our *objective* for this experiment is to determine whether graph theory measures of intrinsic MEG activity correlate with cognitive dysfunction in PD. We *hypothesize* that loss of small-world architecture contributes to cognitive dysfunction in PD through loss of local efficiency and increased randomness. To test this hypothesis, 25 PD subjects with MCI and 25 with normal cognition will undergo neuropsychological testing and a resting MEG scan for analysis for this aim. MEG and neuropsychological testing may be done on the same day or separate days, not to exceed 1 week in between. We will use graph theory measures to model the

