AIM 3 Rationale and Design: rTMS can improve cognition in PD without dementia⁵², PD with depression⁸⁰, older adults¹²² and in AD¹²³ but has not been tested in PD-MCI. Given the need for improved cognitive treatments and possible differences in rTMS effects on PD-MCI pathophysiology it is important to specifically test rTMS in this population. Prior studies as well as our own pilot data suggest that rTMS modulates cortical connectivity,^{16,17} thus rTMS provides not only a potentially effective intervention but an important causal test of our associative data and theoretical link between cortical connectivity and cognitive dysfunction in PD. Our *clinical objective* for this experiment is to determine whether rTMS improves cognitive outcomes in PD-MCI. Our *mechanistic objective* is to determine whether rTMS normalizes patterns of cortical connectivity. We *hypothesize* that high-frequency bifrontal rTMS will partially normalize patterns of cortical connectivity linked to frontal nodes and will improve cognitive measures. To test this hypothesis 55 PD-MCI subjects will be randomized to a 10-day course of real or sham bifrontal high frequency rTMS. We will measure cognitive and MEG outcomes pre-treatment and on the day of the last treatment (neuropsych testing and MEG procedures may be separated by 1 day if patient is fatigued) and repeat cognitive measures 28 days post rTMS to assess the durability of cognitive changes.

TMS: TMS will be administered using a 70-mm diameter air-cooled figure-of-8 coil and SuperRapid² Magstim Stimulator. We will first define the subject's resting motor threshold (MT) by localizing the hand area of motor cortex and determining the minimal TMS amplitude needed to produce a motor-evoked potential of 50 microV on 4 of 8 trials measured by EMG over the first dorsal interosseous muscle (Biopac, Goleta, CA). Once the MT is determined, repetitive pulses will be delivered to the right and left pre-frontal cortex (Brodmann area 46) using a frameless stereotactic navigation system and the subject's MRI in Brainsight software. Depending on our preliminary results from Aim 1, we may change our target if it is evident that a particular frontal node shows high clustering within beta or theta frequency bands. This type of targeting based on functional data has been previously performed and may enhance TMS effects on intrinsic connectivity.¹⁶ Stimuli will be delivered at 20 Hz at 90% rMT for 25 trains of 30 pulses per train, inter-train

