interval of 30 seconds for a total of 750 pulses per hemisphere, which is well within the most recent international TMS safety guidelines.¹²⁹ This dose and duration of rTMS is based on physiological studies of healthy adults and treatment studies of cognition in PD and Alzheimer’s disease.^{52, 123} Side of first stimulation (left vs right hemisphere) will be counterbalanced across subjects. Sham stimulation will be delivered using a sham coil fitted with electrodes to mimic both the auditory and somatic sensation of real TMS as I have performed in prior TMS trials.¹⁹

Schedule of Procedures

	Baseline Procedures ²	← 2 weeks →			28 days post-rTMS Session 10 ¹
		rTMS Session 1 ¹	rTMS Sessions 2-9 ¹	rTMS Session 10 ¹	
Informed consent	X				
MRI (anatomical and optional functional scans)	X				
MEG	X			X ¹	
Neuropsych tests	X			X ¹	X ¹
rTMS (real or sham) ¹		X ¹	X ¹	X ¹	
Randomization to real or sham TMS ¹	X				

¹PD-MCI subjects only

²Baseline procedures to be completed within 1 week of rTMS Session 1

D. Description, Risks and Justification of Procedures and Data Collection Tools:

PD-MCI and mild dementia patients may be considered a vulnerable population due to cognitive dysfunction but are necessary to answering our research questions. We are cognizant of this issue and will carefully assess potential participant’s understanding of the study, particularly of study activities and risks. If there are any concerns on the part of the investigator or potential participant, we will require that their guardian participate in the consenting process and sign an informed consent. We will also require that PD-MCI subjects give consent, or at minimum assent if fully informed consent is not possible. Our protocol and consent forms will be approved by our local IRB before approaching any potential subjects.

After enrollment and screening assessment, PD and PD-MCI subjects will undergo neuropsychological testing, magnetoencephalography (MEG) recordings, and MRI. PD-MCI subjects will then be randomized in a 1:1 ratio to real or sham TMS groups using MAPLE 9.0 software (Waterloo, Canada). Baseline neuropsychological testing, MEG, and MRI may be performed over multiple days, but all will be completed within 1 week and within 1 week of first TMS session for PD-MCI subjects.

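### Aim 1 plans to analyse 25 of the 55 cognitively impaired patients, although all 55 have the same baseline MEG and cognitive data; using them all is a cheap gain in precision.

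*Combined protocol and SAP*

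**What the plan says.** Section IV.B enrols 25 PD patients without cognitive impairment and "55 PD subjects over the age of 40 with MCI or mild dementia", 80 in all. For Aim 1, section IV.C states that "25 PD subjects with MCI and 25 with normal cognition will undergo neuropsychological testing and a resting MEG scan for analysis for this aim". The Aim 1 sample-size paragraph in section IV.F builds on the same 50 and takes 45 as evaluable, "allowing for 5 drop-outs and/or unusable data-sets from the original 50".

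The 55 impaired patients are also the Aim 3 trial population. For them section IV.C states: "We will measure cognitive and MEG outcomes pre-treatment and on the day of the last treatment". Section IV.D gives both groups one baseline battery: "PD and PD-MCI subjects will undergo neuropsychological testing, magnetoencephalography (MEG) recordings, and MRI". The Schedule of Procedures does not confine baseline MEG or testing to a subgroup.

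The time limits agree. Aim 1 says "MEG and neuropsychological testing may be done on the same day or separate days, not to exceed 1 week in between". Section IV.D lets the baseline tests run over several days, "but all will be completed within 1 week and within 1 week of first TMS session for PD-MCI subjects".

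The only sign of an early use of Aim 1 data is in the TMS paragraph of section IV.C: "Depending on our preliminary results from Aim 1, we may change our target".

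**The concern.** Aim 1 asks whether small-worldness is associated with the MDRS total score. Its primary analysis is a Spearman correlation per frequency band, followed by linear regression with age and motor severity. Neither step needs equal groups. Yet the planned set stops at 25 impaired patients, while 30 more contribute the same measurements, taken before any stimulation and within the time limit that Aim 1 sets for itself. No reason is given for stopping at 25.

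At stake is precision in an aim whose sample is small. The extra data need no new patient, visit or scan, because Aim 3 must collect and process them anyway.

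**Working it through.** **Inputs.** Aim 1 set 50, evaluable 45, so loss is 5/50 = 10% (IV.F). Enrolled 25 + 55 = 80 (IV.B). Six frequency bands (MEG Data Processing, IV.A). Significance 0.05, taken as two-sided because the plan does not say. r = 0.35 is an illustration chosen here, not a figure from the plan.

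**Are the 25 part of the 55?** This is inferred. A separate group would need 25 + 25 + 55 = 105 enrolled, against 80. Section IV.D also sends PD-MCI subjects on to randomisation without exception.

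**Evaluable numbers.** 80 × 0.9 = 72. Left out: 30 × 0.9 = 27, which is 72 − 45.

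**The plan's own figure.** Section IV.F states r = 0.18 with 80% power at 45. Using Fisher's z with the Spearman variance factor, SE = √(1.06/(n − 3)) and detectable r = tanh((1.960 + 0.842) × SE).
- n = 45: SE = √(1.06/42) = 0.159; tanh(2.802 × 0.159) = 0.418. Without the factor it is 0.407.
- Power at r = 0.18 and n = 45 is 21%. For 80% power, n = 1.06 × (2.802/0.182)² + 3, about 255.

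The stated 0.18 therefore does not reproduce. That is a separate error.

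**Gain by formula (one bivariate population, before FDR control).**
- n = 72: SE = √(1.06/69) = 0.124; detectable r = tanh(2.802 × 0.124) = 0.334.
- Power at r = 0.35 (Fisher z = 0.365): at n = 45, 0.365/0.159 = 2.30, giving 63%; at n = 72, 0.365/0.124 = 2.95, giving 84%.
- At 0.05/6, as a worst case for the six bands: detectable r goes from 0.50 to 0.41, and power at r = 0.35 from 37% to 62%.

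**Gain by source of the association.** The extra patients all join one group, so the formula can overstate the benefit. The Spearman test was simulated with 22 unimpaired and 23 impaired, then with 22 and 50. The MDRS gap between groups was 1 to 3 SD, and r = 0.35 was defined at a 1:1 mix.

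| Source of association | Power, n = 45 | Power, n = 72 |
|---|---|---|
| Wholly within groups | about 60% | 83–90% |
| Half between groups | about 62–67% | 80–84% |
| Wholly between groups | about 68–71% | 74–77% |

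In the last row, the correlation needed for 80% power moves from about 0.38–0.39 to about 0.36–0.37, a gain of about 0.02.

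**If only MCI patients are added.** The MCI share of the 55 is not given. Evaluable n = (25 + 55 × share) × 0.9.
- Share 50%: about 47, detectable r 0.41.
- Share 70%: about 57, detectable r 0.37 by formula.
- Share 100%: 72, the full gain.

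**At the plan's r = 0.18.** Power rises from 21% to 31% by formula. If the association is wholly between groups, it rises from about 22% to 25%.

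**The case against.** A fixed, prespecified sample is not an error in itself, and no sentence forbids using later baseline data. The design also suggests reasons for 25 and 25. Aim 1 results may inform the rTMS target, so some of them are needed early. Aim 2 reuses the same data to classify patients with and without MCI, where balance is convenient. Neither reason is stated as the basis for the number. The first explains an early look and the second concerns another aim; neither explains leaving later baselines out of the final Aim 1 correlation.

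The population objection is stronger. Aim 1 says MCI, while section IV.B enrols MCI or mild dementia and names the two separately. Aim 3 calls all 55 PD-MCI, so the label is used loosely, but pooling everyone may still widen the population that Aim 1 names. This stands. It is why the restricted analysis belongs beside the pooled one, and why the gain must be given as a range that starts near zero.

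It also stands that the formula's 0.42 may not be set against a detectable correlation from a between-group scenario. Like for like, that scenario gains about 0.02.

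A reader might infer that, with no selection rule, the 25 could be picked after the data are seen. Nothing in the documents suggests this; the unstated rule is a missing detail.

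**Conclusion.** The point holds as a cheap improvement, not as a flaw that invalidates Aim 1. About 27 usable baseline datasets are left out of an analysis that could use them, with no reason given. Power rises in every scenario examined. At r = 0.35 the gain is about 20 points by formula (63% to 84%), somewhat less if half the association lies between groups, and about 5 to 7 points if all of it does. An MCI-only set gains between almost nothing and the full amount.

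This rests on four assumptions: the 25 lie within the 55; the plan's 10% loss applies to all 80; tests are two-sided; and the figures are before FDR control unless marked.

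Two further readings are not supported. One is that the larger set makes the sample-size statement true: at r = 0.18 power stays at about 25–31% in the formula and the half- or wholly-between-group cases. The other is that Aim 2 is too small: the documents do not show that, and no change to Aim 2 is claimed.

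**What to change.** In sections IV.C and IV.F:
- Define the final Aim 1 analysis set as all enrolled subjects with usable baseline MEG and MDRS (up to 80, about 72 at 10% loss).
- Report beside it the same analysis restricted to unimpaired plus MCI patients, and record at baseline whether each impaired patient has MCI or mild dementia.
- If an early 25/25 set informs targeting, fix it by enrolment order and label its results preliminary.
- State that Aim 2 keeps its own set, since it is now defined through the Aim 1 data.
- If 25/25 remains the final Aim 1 set, give the reason and the selection rule.
- Correct the r = 0.18 statement separately.

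The cost is wording, plus use of MEG files that Aim 3 processes anyway. The downsides are that final Aim 1 results wait for Aim 3 enrolment, the groups become 25:55, and the case mix may include more mild dementia than Aim 1 names.
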